6.8.5. Additional Risks

6.8.5.1. Bleeding Events

Bleeding events are a potential risk for bintrafusp alfa (refer to IB).

For all participants:

For Grade ≥ 2 tumor bleeding, study treatment must be held until the event recovers to Grade ≤ 1 . If a Grade ≥ 3 tumor bleeding event has been observed, regardless of causality with the study intervention, upon resumption of the study intervention the bintrafusp alfa dose should be reduced to 600 mg Q2W. Once there is stable resolution and no recurrence of bleeding on the reduced dose, the investigator is encouraged to communicate with the medical monitor regarding a potential dose re-escalation after careful benefit-risk assessment. Treatment should be permanently discontinued if the investigator considers the participant to be at risk for additional severe bleeding. In case of a rapid decrease of hemoglobin (Hgb), see [Table A8](#) (Management of Hematologic irAEs in Patients Treated with ICPis) in Section [10.9](#).

If a Grade ≥ 3 non-tumor bleeding event is observed, study treatment must be permanently discontinued unless an alternative explanation can be identified (such as concomitant use of antithrombotic agents, traumatic event, etc.). In case of alternative explanations for the Grade ≥ 3 bleeding event, study treatment should be held until the event recovers to Grade ≤ 1 . If a Grade ≥ 3 bleeding event is observed, regardless of causality with the study intervention, upon resumption of study intervention, the bintrafusp alfa dose should be reduced to 600 mg Q2W. Once a Hgb decrease recovers to Grade ≤ 1 or there is stable resolution and no recurrence of bleeding on the reduced dose, the investigator is encouraged to communicate with the medical monitor regarding a potential dose re-escalation after careful benefit-risk assessment. The dose of bintrafusp alfa may be re-escalated to full dose (1200 mg Q2W) once Hgb is stabilized without further need for blood transfusion in the subsequent cycles. The timing of re-escalation will be determined on a case-by-case basis. See Section 6.8.4 regarding the stabilization of anemia.

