For Grade 4 non-tumor bleeding, treatment must be permanently discontinued if no alternative explanation is identified. In case of rapid decrease of Hgb, such as a decrease greater than 2.0 g/dL across a 2-week period, withhold the subsequent cycles of study intervention until Hgb is stabilized and do a thorough assessment of bleeding (for example, upper and lower gastrointestinal [GI] endoscopy, contrast-enhanced CT scan, etc.). If Grade ≥ 1 bleeding is observed or suspected, withhold the bintrafusp alfa until the bleeding is resolved/controlled and resume the dose of bintrafusp alfa, decreased to 600 mg Q2W. The dose of bintrafusp alfa may be re-escalated to full dose (1200 mg Q2W) once Hgb is stabilized to Grade 1 or baseline without further need for blood transfusion in the subsequent cycles; the investigator is encouraged to communicate with the medical monitor to re-escalate the dose. The timing of re-escalation will be determined on a case-by-case basis. See Section 6.8.4 regarding stabilization of anemia.

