8.0 Hematologic Toxicities	
8.1 Autoimmune hemolytic anemia	
Definition: A condition in which RBCs are destroyed and removed from the blood stream before their normal lifespan is over. Symptoms include weakness, paleness, jaundice, dark-colored urine, fever, inability to do physical activity, and heart murmur.	
Diagnostic work-up	
History and physical examination (with special consideration of history of new drugs and insect, spider, or snake bites)	
Blood chemistry, CBC with evidence of anemia, macrocytosis, evidence of hemolysis on peripheral smear; LDH, haptoglobin, bilirubin, reticulocyte count, free Hgb DIC panel, which could include PTNIR infectious causes	
Autoimmune serology	
Paroxysmal nocturnal hemoglobinuria screening	
Direct and indirect bilirubin; LDH; direct agglutinin test; and if no obvious cause, bone marrow analysis, cytogenetic analysis to evaluate for myelodysplastic syndromes	
Evaluation for viral/bacterial (mycoplasma, etc) causes of hemolysis studies	
Protein electrophoresis, cryoglobulin analysis	
Work-up for bone marrow failure syndrome if refractory, including B12, folate, copper, parvovirus, FE, thyroid, infection	
Glucose-6-phosphate dehydrogenase	
Evaluation of common drug causes (ribavirin, rifampin, dapsone, interferon, cephalosporins, penicillins, NSAIDs, quinine/quinidine, fludarabine, ciprofloxacin, lorazepam, diclofenac, etc)	
Assessment of methemoglobinemia	
Grading	Management
G1: Hgb < LLN to 10.0 g/dL; < LLN to 6.2 mmol/L; < LLN to 100 g/L	Continue ICPi with close clinical follow-up and laboratory evaluation
G2: Hgb < 10.0 to 8.0 g/dL; < 6.2 to 4.9mmol/L; <100 to 80 g/L	Hold ICPi and strongly consider permanent discontinuation Administer 0.5-1 mg/kg/d prednisone equivalents
G3: Hgb <8.0 g/dL; <4.9 mmol/L; <80 g/L; transfusion indicated	Permanently discontinue ICPi Should use clinical judgment and consider admitting the patient Hematology consult Prednisone 1-2 mg/kg/d (oral or IV depending on symptoms/speed of development) If worsening or no improvement, 1-2 mg/kg/d prednisone equivalents and permanently discontinue ICPi treatment Consider RBC transfusion per existing guidelines; do not transfuse more than the minimum number of RBC units necessary to relieve symptoms of anemia or to return a patient to a safe Hgb range (7-8 g/dL in stable, noncardiac inpatients) Should offer patients supplementation with folic acid 1 mg once daily

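### Protocol Section 6.8.5.1 gives two unreconciled instructions for a rapid hemoglobin fall, and does not state the scope of its Grade 1 or higher bleeding sentence

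*Protocol*

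**What the plan says.** Section 6.8.5.1 is addressed to all participants and has three paragraphs.

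- **Tumor bleeding.** Treatment is held from Grade 2 until recovery to Grade 1 or less. From Grade 3 it resumes at 600 mg Q2W. It is stopped permanently if the investigator sees a risk of further severe bleeding. The paragraph ends: "In case of a rapid decrease of hemoglobin (Hgb), see [Table A8](#) (Management of Hematologic irAEs in Patients Treated with ICPis").
- **Grade 3 or higher non-tumor bleeding.** Treatment is stopped permanently unless there is an alternative explanation. If there is one, it is held and later resumed at 600 mg Q2W.
- **Grade 4 non-tumor bleeding.** Treatment is stopped permanently if there is no alternative explanation. The same paragraph continues: "In case of rapid decrease of Hgb, such as a decrease greater than 2.0 g/dL across a 2-week period, withhold the subsequent cycles" until Hgb is stabilized, and "do a thorough assessment of bleeding". The next sentence is conditional on Grade 1 or higher bleeding: if such "bleeding is observed or suspected, withhold the bintrafusp alfa until the bleeding is resolved/controlled and resume the dose of bintrafusp alfa, decreased to 600 mg". Return to 1200 mg is possible "once Hgb is stabilized to Grade 1 or baseline without further need for blood transfusion in the subsequent cycles".

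Table A8 (Appendix 9) covers hematologic immune-related events by diagnosis. Its section 8.1, autoimmune hemolytic anemia, is the only block graded directly by Hgb value:

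- Grade 1, below the lower limit of normal (LLN) to 10.0 g/dL: "Continue ICPi with close clinical follow-up and laboratory evaluation".
- Grade 2, below 10.0 to 8.0 g/dL: hold, strongly consider stopping permanently, and give prednisone.
- Grade 3, "G3: Hgb <8.0 g/dL; <4.9 mmol/L; <80 g/L; transfusion indicated": stop permanently.
- Grade 4, life-threatening: stop permanently.

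**The concern.** The same trigger appears twice in one subsection, with two destinations. An investigator who follows the first sentence goes to a table that either does not address the event or, at 8.1, acts on the absolute Hgb level. One who follows the second acts on the size and speed of the fall. Two sites could therefore treat the same participant differently, and both could cite the protocol.

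The Grade 1 sentence adds a second uncertainty: whether it is a general rule for all bleeding or only a step in the work-up of a rapid fall.

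Section 6.7 bars dose modification except as Section 6.8.5 allows for bleeding, so this is the controlling text. The main stake is participant safety. The secondary stake is descriptive. Holds, reductions and discontinuations feed relative dose intensity (SAP Sections 12 and 12.1) and the counts of adverse events leading to interruption or discontinuation (SAP Section 14.1.2).

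**Working it through.** The plan has no figure to reproduce. The check puts the instructions side by side and runs illustrative Hgb falls through both.

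**Inputs.** The example threshold is a fall of more than 2.0 g/dL across 2 weeks (Section 6.8.5.1). The bands and actions are those of Table A8, section 8.1. The documents give no LLN; 12 to 13.5 g/dL is assumed.

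**Step 1: the rapid fall.** Fall = start minus end.

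| Hgb over 2 weeks (g/dL) | Fall | Table A8, 8.1, if applied | Grade 4 non-tumor paragraph | Agree? |
|---|---|---|---|---|
| 13.0 to 10.5 | 13.0 − 10.5 = 2.5 | Grade 1: continue | Withhold until stabilized | No |
| 12.0 to 9.5 | 12.0 − 9.5 = 2.5 | Grade 2: hold, strongly consider permanent stop, prednisone | Withhold until stabilized | Both hold; they differ on what follows |
| 10.5 to 7.9 | 10.5 − 7.9 = 2.6 | Grade 3: permanent stop | Withhold until stabilized | No |

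All three falls exceed 2.0 g/dL. Only the first row depends on the LLN. Anywhere in the assumed range, 10.5 is Grade 1. With an LLN at or below 10.5 the table would assign no grade and still call for no hold. The second and third rows do not depend on it.

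**Step 2: where 600 mg comes from.** It is not attached to the rapid fall. It comes from the following sentence, whose condition is Grade 1 or higher bleeding observed or suspected. The subsection states no resumption dose for a rapid fall in which no bleeding is found or suspected.

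**Step 3: scope of the Grade 1 sentence.** There are two readings, and they exclude each other.

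- *It stands alone.* Grade 1 tumor bleeding is not held under the tumor paragraph but is held and resumed at 600 mg under this sentence (600/1200 = 50% of the dose). That conflicts with the Grade 2 hold and Grade 3 reduction thresholds.
- *It applies only after a rapid fall.* There is then no general Grade 1 rule. The sentence does add a reduction trigger below Grade 3: Grade 2 tumor bleeding with a rapid fall would resume at 600 mg, whereas the tumor paragraph names no reduced dose for Grade 2. It also has no upper bound. Read literally, it covers Grade 3 or 4 non-tumor bleeding without an alternative explanation, which the same subsection says must lead to permanent discontinuation.

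**Step 4: weight in the analysis.** With about 25 treated participants, one participant classified differently moves a percentage by 1/25 = 4 percentage points.

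**The case against.** The strongest defense is that Table A8 is entered by diagnosis. Section 8.1 is defined by red-cell destruction and carries a hemolysis work-up, so a fall caused by bleeding does not belong there. Table 4 in Section 6.8.4 already separates suspected hemolysis from suspected bleeding. On this view the reference means only that an immune cause should be considered. That is a sensible reading, but the sentence does not say it: it names the whole table, sits in a paragraph about tumor bleeding, and sets no condition on cause. Section 6.8.4 guides evaluation and does not settle the dose action.

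A second defense is that the Table A8 reference covers tumor bleeding and the withhold rule covers non-tumor bleeding. The paragraph positions allow this, but neither sentence states it. The second sentence also orders a search for bleeding, so the source may be unknown when the hold is decided.

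A third is that the Grade 1 sentence is plainly part of the rapid-fall work-up. Its position and its Hgb-based re-escalation condition favor that, so a general Grade 1 rule is not proven.

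Four stronger inferences are tempting and are not supported:

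- *That 600 mg is the rule for a rapid fall as such.* It is conditional on bleeding.
- *That any transfusion leads to permanent discontinuation.* The Table A8 wording on transfusion belongs to Grade 3 hemolytic anemia.
- *That participants who enter with Hgb of 9.0 to 9.9 g/dL, as Section 5.1 allows, are already caught at Grade 2.* A baseline value is neither a rapid fall nor hemolysis.
- *That the Grade 1 conflict and a 600 mg rapid-fall rule both hold.* They rest on opposite readings of one sentence.

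The reach is also limited. Enrollment has ceased with 25 participants treated, and those who continue after data cut-off are managed by local standard of care. The affected outputs are descriptive, and no effect on the response rate is shown.

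**Conclusion.** The point holds as an unreconciled pair of instructions and a sentence of unstated scope. It is not two proven incompatible dosing rules. If Table A8 section 8.1 is the part meant, the actions differ at Grade 1 (continue against withhold, assuming an LLN above 10.5 g/dL in the example) and at Grade 3 (permanent discontinuation against withholding until stabilized). If another part of the table is meant, the reference gives no usable instruction for a rapid fall.

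The Grade 1 sentence needs attention on either reading. Standing alone, it conflicts with the tumor-bleeding thresholds. Nested, it adds a reduction trigger below Grade 3 and is not squared with the permanent-discontinuation rules.

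This should be corrected because it bears on the safety of participants still receiving treatment. It does not threaten the primary analysis. No view is given on which dose or clinical rule is right.

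**What to change.** Reword Section 6.8.5.1 in three places:

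1. Reconcile the two rapid-fall sentences so that a rapid Hgb decrease leads to one instruction. If tumor and non-tumor bleeding are meant to differ, say so.
2. Name the part of Table A8 that is meant and when it applies, for example whether only when hemolysis is suspected.
3. State whether the Grade 1 or higher sentence applies only after a rapid Hgb decrease or to all bleeding. Align it with the Grade 2 hold, the Grade 3 reduction and the permanent-discontinuation rules for non-tumor bleeding.

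The choice of rule belongs to the sponsor and its clinical team. The cost is rewording of one subsection and one cross-reference, with no added tests.

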6.8.5.2. Alterations in Wound Healing or Repair of Tissue Damage

Due to the involvement of TGF- β in tissue and skin repair, alterations in wound healing or repair of tissue damage is considered an important potential risk. No relevant event is reported in the ongoing bintrafusp alfa clinical studies. Monitoring of any surgical wounds while on study is recommended. In general, a 2-week delay from treatment is recommended following minor surgery and 4-week delay for major surgery, but cases should be discussed with the medical monitor.

6.8.5.3. Embryofetal Toxicity

Embryo-fetal toxicities are a known risk of the PD-1/L1 targeting class. Animal models link the PD-1/L1 signaling pathway with maintenance of pregnancy through induction of maternal immune tolerance to fetal tissue. Embryo-fetal and reproductive toxicities have also been investigated in animal models for a humanized monoclonal antibody targeting TGF- β 1. At doses as high as 30 mg/kg, no maternal reproductive toxicity or embryo-fetal lethality were observed in rabbits (Hilbush, 2016). To mitigate these potential risks, pregnant participants are excluded from the study, and all participants of childbearing/conceiving potential must use highly-effective contraception.

6.9. Intervention After the End of the Study

Study participants that continue to benefit from study intervention beyond the DCO date will continue to have access to study intervention until the EOS as defined in Section 4.7. There is no planned intervention following the EOS.

The investigator is responsible for ensuring that consideration has been given to the post-study care of the participant's medical condition.

Refer to the SoA (Table 1) for follow-up assessments of participants who are to be followed for disease progression and survival after they permanently discontinue from bintrafusp alfa until the DCO date and from the DCO date to the EOS.

6.10. Continued Access to Study Intervention After Data Cut-off

Participants who are considered to be deriving benefit from study intervention by the investigator, with agreement with the GSK medical monitor, and who do not meet any protocol-defined treatment discontinuation criteria may continue to receive study intervention after the DCO date for up to 2 years after their first dose or up to 2 years from time of confirmed CR. Please see the SRM for details regarding drug resupply.

Drug accountability data will also be collected at site visits.

7. DISCONTINUATION OF STUDY INTERVENTION AND PARTICIPANT DISCONTINUATION/WITHDRAWAL

7.1. Discontinuation of Study Intervention

In some instances, it may be necessary for a participant to permanently discontinue study intervention for any of the following reasons:

- A participant may discontinue from the study intervention at any time at his/her own request (i.e., withdrawal of consent), and without giving a reason.
- Occurrence of an exclusion criterion, which is clinically relevant and affects the participant's safety, if discontinuation is considered necessary by the investigator and/or sponsor.
- A participant may be discontinued at any time at the discretion of the investigator for safety, behavioral, compliance, or administrative reasons (See Section 6.8 for TEAEs and AEs of Interest that require treatment discontinuation).
- Confirmed PD per RECIST 1.1, with the exception that participants receiving treatment may continue past PD if the participant's ECOG PS has remained at least stable, and if in the opinion of the investigator, the participant will benefit from continued treatment (See Section 7.1.1).
- Unacceptable toxicity.
- Some TEAEs and AEs of Interest require withdrawal from treatment (Section 6.8).
- Drug must not be given to a known pregnant participant (refer to [Appendix 4](#)).
- Use of a prohibited concomitant drug, as defined in Section 6.6.1, where the predefined consequence is withdrawal from the study intervention.

The SoA ([Table 1](#)) specifies the data to collect at study intervention discontinuation, 28-day safety follow-up, follow-up, and any additional evaluations that need to be completed.

In case of discontinuation from the study intervention:

- The day of End-of-Treatment will correspond to the day of withdrawal (or within 7 days).
- An attempt should be made to perform all assessments scheduled for the End-of-Treatment visit if possible. If not possible, the most clinically relevant assessments and appropriate eCRFs for the End-of-Treatment visit should be prioritized as feasible.
- Participants will be asked to continue Safety and Survival Follow-up, which includes the collection of data on survival, and subsequent anti-cancer therapy. After completion of the follow-up period or after the End-of-Treatment visit, whichever is applicable, the appropriate eCRF section for Study Termination must be completed.

- If the participant is enrolled into a new study or any new therapy post-withdrawal from study intervention, the Safety Follow-up visit should be scheduled prior to the start of the new treatment irrespective of the 28-day Safety Follow-up period.
- For participants discontinuing from study treatment after the DCO date for final analysis, no study-specific visits or eCRF completion will be required per Section 8.2.

7.1.1. Disease Progression

Disease progression must be assessed by the investigator and documented in the participants CRF. Before stopping the treatment, progressive disease should be confirmed by imaging at least 4 weeks after progression according to RECIST v1.1 unless:

- Study intervention is not tolerated, or
- ECOG PS is declining, or
- The investigator considers an alternative intervention to be in the best interest of the study participant.

The decision to continue treatment beyond confirmed PD should be discussed with the medical monitor and documented in the study records if the investigator believes that the participant would continue to benefit according to [Table 1](#).

Participants who continue beyond progression will be evaluated for further tumor response as per the protocol schedule. Treatment should be discontinued upon documentation of further, unequivocal, disease progression or upon meeting any other criteria for discontinuation.

[figure not shown]
7.1.2. Liver Chemistry Stopping Criteria

Liver chemistry stopping, and increased monitoring criteria have been designed to assure participant safety and evaluate liver event etiology.

Discontinuation of study intervention for abnormal liver tests is required when:

- a participant meets one of the conditions outlined in [Appendix 6](#).
- when in the presence of abnormal liver chemistries not meeting protocol-specified stopping rules, the investigator believes study intervention discontinuation is in the best interest of the participant.

Figure 2 Phase I/II Liver Chemistry Stopping and Increased Monitoring Algorithm including Participants WITH documented liver metastases/tumor infiltration at baseline AND entry criteria ALT >2.5x ULN but \leq 5x ULN

Liver Safety Required Actions and Follow up Assessments Section can be found in [Appendix 6](#).

7.1.2.1. Study Intervention Restart or Rechallenge after liver stopping criteria

Study intervention restart or rechallenge after liver chemistry stopping criteria are met by any participant in this study is not allowed.

7.1.3. QTc Stopping Criteria

- The *same* QT correction formula *must* be used for *each individual participant* to determine eligibility for and discontinuation from the study. This formula may not be changed or substituted once the participant has been enrolled.
 - For example, if a participant is eligible for the protocol based on QTcF, then QTcF must be used for discontinuation of this individual participant as well.
 - Once the QT correction formula has been chosen for a participant's eligibility, the *same formula* must continue to be used for that participant *for all QTc data being collected for data analysis*. Safety ECGs and other non-protocol specified ECGs are an exception.

- The scheduled QTc evaluations should be based on single ECG readings.
- Withdrawal of participants is to be based on an average QTcF value of triplicate ECGs. If a single ECG demonstrates a prolonged QTcF interval, then obtain 2 more ECGs over a brief period (e.g., 5-10 minutes) and then use the averaged QTcF values of the 3 ECGs to determine whether the participant should be discontinued from the study.
 - If a participant meets either of the following criteria, they must be discontinued from study treatment: QTcF >500 msec OR Change from baseline of QTcF >60 msec.
 - For participants with underlying bundle branch block and baseline QTcF <450 msec, discontinue if QTcF is >500 msec. For participants with baseline QTcF 450-480 msec, discontinue if QTcF is >530 msec.
 - QTcF = QT duration corrected for heart rate by Fridericia's formula. See the SoA ([Table 1](#)) for data to be collected at the time of treatment discontinuation and follow-up and for any further evaluations that need to be completed.

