10. Active infection requiring systemic therapy.
11. Received any live vaccine within 30 days prior first dose of intervention.
12. Known history of positive test for human immunodeficiency virus (HIV) with the exception of participants with CD4+ T-cell (CD4+) counts ≥ 350 cells/ μ L and no history of AIDS-defining opportunistic infections.
13. Active hepatitis B virus (HBV) (HBV surface antigen-positive).
14. Active hepatitis C virus (HCV) infection, or positive HCV antibody, with the exception of participants that (1) have HCV viral load below the limits of

quantitation and (2) completed curative antiviral therapy or are receiving and compliant with antiviral therapy

15. History or evidence of cardiac abnormalities within the 6 months prior to first dose of intervention which include:

- Serious, uncontrolled cardiac arrhythmia or clinically significant electrocardiogram abnormalities including second degree (Type II) or third-degree atrioventricular block or QTcF interval >450 msec (or QTcF >480 msec for participants with bundle branch block).
- Cardiomyopathy, myocardial infarction, acute coronary syndromes (including unstable angina pectoris), coronary angioplasty, stenting or bypass grafting
- Congestive heart failure (Class II, III, or IV) as defined by the New York Heart Association functional classification system
- Symptomatic pericarditis

16. Participants with history of bleeding diathesis or recent major bleeding events considered by the investigator as high risk for investigational drug treatment are also excluded.

17. Any other serious or uncontrolled medical disorder that, in the opinion of the investigator, may increase the risk associated with study participation or study drug administration, impair the ability of the participant to receive protocol therapy, or interfere with the interpretation of study results.

Prior/Concomitant Therapy

- Received prior systemic anti-cancer therapy within 2 weeks prior to study treatment.
- Received prior therapy with an anti-PD-1, anti-PD-L1, anti-PD-L2, anti-CD137, or anti-Cytotoxic T-lymphocyte-associated antigen-4 (CTLA-4) antibody (including ipilimumab or any other antibody or drug specifically targeting T-cell co-stimulation or checkpoint pathways).
- Received prior therapy targeting TGF- β (e.g., Galunisertib, etc.).
- Received radiation therapy (or other non-systemic disease therapy) within 2 weeks prior to study treatment.

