9.2. Sample Size Determination

A total of 25 participants will receive bintrafusp alfa.

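### Protocol 7.1.3 gives QTcF stopping limits that disagree, without saying which prevails or whether the >60 msec change limb covers bundle branch block

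*Protocol*

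**What the plan says.** Entry is governed by exclusion criterion 15 (protocol section 5.2), which excludes a "QTcF interval >450 msec (or QTcF >480 msec for participants with bundle branch block". Participants with bundle branch block can therefore enter with a QTcF up to and including 480 msec. Those without block can enter up to and including 450 msec.

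Section 7.1.3 first fixes the value to be judged: "Withdrawal of participants is to be based on an average QTcF value of triplicate ECGs". Two sub-bullets at the same level follow.

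- General rule, for a participant who meets either limit: "they must be discontinued from study treatment: QTcF >500 msec OR Change from baseline of QTcF >60 msec".
- Second bullet, first sentence: "For participants with underlying bundle branch block and baseline QTcF <450 msec, discontinue if QTcF is >500 msec".
- Second bullet, second sentence: "For participants with baseline QTcF 450-480 msec, discontinue if QTcF is >530 msec".

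No word links the two bullets. The second is not introduced as an exception, a replacement or an addition. Neither of its sentences mentions change from baseline, and its second sentence does not repeat the bundle branch block condition.

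**The concern.** The general rule is mandatory and names no excepted group, yet the second bullet sets different limits for people who also fall under the general rule. An investigator who sees a QTcF of 515 msec in a participant whose baseline was 475 msec finds one bullet that requires stopping and another whose limit has not been reached. The measurement basis does not explain the difference, because both bullets sit under the same triplicate-average instruction.

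The question stays open although enrollment has ended. Protocol sections 6.10 and 8.2 allow treatment after the data cut-off only if no protocol-defined discontinuation criterion is met. Inside the overlap, the text does not settle whether that condition is satisfied, or whether continued dosing follows the protocol.

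**Working it through.** No sample size, power or error rate is involved, so there is no figure in the plan to reproduce. The check compares the rules as written.

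**Inputs.** Let b be baseline QTcF and Q the on-study triplicate average, both in msec. Entry limits come from criterion 15; stopping limits come from section 7.1.3.

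- General rule: stop if Q > 500 or Q − b > 60.
- Second bullet: stop if Q > 500 (block, b < 450), or if Q > 530 (b from 450 to 480).

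**Baseline 450-480.** The general rule stops at Q > 500. The second bullet stops at Q > 530. They disagree for 500 < Q ≤ 530, a band of 530 − 500 = 30 msec at every baseline in this range. Any Q above 530 is already above 500, so if both bullets apply the >530 limit never decides anything.

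**Bundle branch block, baseline below 450.** The absolute limits agree at 500, so only the change limb can differ. It is reached first when b + 60 < 500, that is, when b < 440. The bullets then disagree for b + 60 < Q ≤ 500, a band of 440 − b msec: 20 msec at b = 420 and 40 msec at b = 400. For b from 440 to 449 there is no disagreement.

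**Three possible readings.** The table gives the highest QTcF that does not require stopping under each. Rows below 450 refer to participants with block.

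| Baseline | A: both bullets apply | B: second bullet replaces only the >500 limb | C: second bullet replaces the whole general rule |
|---|---|---|---|
| 400 | 460 | 460 | 500 |
| 420 | 480 | 480 | 500 |
| 440 | 500 | 500 | 500 |
| 450 | 500 | 510 | 530 |
| 460 | 500 | 520 | 530 |
| 470 | 500 | 530 | 530 |
| 480 | 500 | 530 | 530 |

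Formulas:

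- A is min(500, b + 60).
- B is min(500, b + 60) below 450 and min(530, b + 60) from 450 to 480.
- C is 500 below 450 and 530 from 450 to 480.

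B and C therefore still differ by 470 − b msec for baselines from 450 up to, but not including, 470. That is 20 msec at 450, 10 msec at 460 and nothing from 470. Under C the rise allowed before stopping is 530 − b: 80 msec at 450, 60 at 470 and 50 at 480.

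**Examples.**

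- Baseline 475, on-study 515 (+40): A stops; B and C do not.
- Baseline 455, on-study 525 (+70): A and B stop; C does not.
- Block, baseline 420, on-study 490 (+70): A and B stop; C does not.

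**Direction.** In a comparison in whole msec at 16 baselines from 400 to 480, no case was found where the second bullet stops and the general rule does not. The disagreement runs one way only.

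**The case against.** The strongest reply is that the second bullet is plainly meant as an exception. It follows the general rule directly, and it mirrors the separate entry limit for block in criterion 15. If the general rule also governed these participants, the bullet would do no work: its >500 sentence would repeat the general limit and its >530 sentence could never operate. A reading that gives each sentence a purpose is preferable. This is right as a matter of reading, and it settles >500 against >530. It does not settle B against C, because the text never says what happens to the >60 msec limb. The protocol does state precedence elsewhere: section 7.1.4 says that the guidance for adverse events of interest overrides its general list, and section 6.7 names its exception expressly.

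A reader might infer that the protocol issues competing stop and continue instructions with equal support, or that stopping someone in the overlap could count as a deviation. The documents do not support either. Section 7.1.3 contains only stopping rules, and continuation is merely implied below a limit. The exception reading has the better support. Sections 7.1 and 7.2 allow stopping at the investigator's discretion, so stopping is permitted on any reading; only continuing is open to dispute.

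Two mitigations also stand. Section 8 sends immediate safety concerns to the sponsor to decide on continuation, and section 6.10 requires the medical monitor's agreement for dosing after the cut-off.

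The missing block condition in the 450-480 sentence is marginal. Given criterion 15, it can affect only a participant without block whose baseline is exactly 450 msec.

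**Conclusion.** The inconsistency is real and should be corrected, but it is a narrow wording fault in a mandatory safety rule. It spans 30 msec (above 500 and up to 530) for baselines of 450-480 msec, and 440 − b msec for bundle branch block with baseline b below 440 msec. Reading the second bullet as an exception removes part of this and leaves the change limb undecided.

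The reach is small. Section 9.2 states: "A total of 25 participants will receive bintrafusp alfa". Enrollment has ceased, and the Schedule of Activities calls for ECGs after screening only as clinically indicated. Assessments revert to local standard of care after the cut-off. The documents do not say how many treated participants have bundle branch block, so the number exposed to the ambiguity could be anywhere from 0 to 25. The SAP (section 14.4) lists ECG values and change from baseline, and the ORR analysis is not directly affected.

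The conclusion rests on the text of section 7.1.3 and criterion 15 alone. It takes no view on which limits are clinically appropriate.

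**What to change.** Reconcile the two bullets of section 7.1.3 with each other and with criterion 15. For each entry group (no block with QTcF up to 450 msec; block with QTcF below 450 msec; block with QTcF 450-480 msec), state which single set of limits applies and whether the change-from-baseline limb is part of it. If the 450-480 sentence is meant only for bundle branch block, repeat that condition in it. The sponsor's clinical team must choose the limits.

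The clarification should reach every site with a participant still on treatment. The drafting is a few lines and needs no new assessments. If it only states what was already intended, a letter to sites may be enough. If any limit changes, it should go through an amendment, which under protocol section 10.1.1 needs ethics committee approval before implementation unless it removes an immediate hazard.
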